3.1.3 Study Visit

All procedures will be conducted over a one day visit. For the 12 participants for the physiological tests (CrCEST evaluation) at CHOP, participants will be taken for the MRI scan in the morning and complete the neurological and biochemical assessments in the afternoon. For the 30 participants enrolled in the MEP protocol at CHOP, this procedure can be arranged either before or after the clinical assessment.

3.1.4 Case Ascertainment

Subjects recruited at the CHOP site are expected to be patients with Friedreich Ataxia followed by [name] through the Neurogenetics clinics at the Children's Hospital of Philadelphia and the Hospital of the University of Pennsylvania. This study will also be posted on clinicaltrials.gov. Additional recruitment may take place by posting notices on the internet through FRDA support and advocacy groups such as Friedreich's Ataxia Research Alliance. Such advertisements would be forwarded to the IRB for approval.

3.1.5 Data sources

The Friedreich Ataxia Clinical Outcomes Study (FACOMS) (CHOP IRB study #01-002609) will serve as a supplemental data source for the study. For participants enrolled in both studies, and who have consented to the optional future use of their data as part of #01-002609, data will be shared from that study for those participants only.

3.2 Controls and Blinding

Not applicable

3.3 Study Duration, Enrollment and Number of Sites

3.3.1 Duration of Study

The total duration for each subject is three years, and initial recruitment will occur over a two year period.

3.3.2 Total Number of Study Sites/Total Number of Subjects Projected

The study will be conducted at 3 investigative sites in the United States. Clinical neurological (Aim 1) assessments and frataxin sample collections (Aim 2) will be carried out at all three sites. Physiological assessments (Aim 3) will only be conducted at CHOP.

The following is a list of sites included in the study:

Children's Hospital of Philadelphia

University of California Los Angeles

University of Florida

The University of Rochester will provide database support

Recruitment will stop when 110 children are enrolled (up to 90 at CHOP, up to 20 at other sites). The majority of subjects will be enrolled at the CHOP site and some will be included to participate in the MEP (n=30) and CrCEST (n=12) measures. A substantial number of participants will be recruited from the ongoing natural history study of all ages, FACOMS, in which some children are already enrolled. [name] sees 30 new FRDA patients per year, with the majority being children. Study advertisements will be sent through the Friedreich Ataxia Research Alliance (FARA) registry, which is a database that includes 141 children living in the United States and over 2000 patients worldwide.

3.4 Study Population

3.4.1 Inclusion Criteria

1) Males or females age 2 to 18 years.

- Genetically confirmed diagnosis of FRDA or clinically confirmed diagnosis of FRDA, pending confirmatory genetic testing through a commercial or research laboratory
- 3) Parental/guardian permission (informed consent) and if appropriate, child assent.
- 4) Weight \geq 10 kg (for the MEP measures only)

3.4.2 Exclusion Criteria

- 1) Inability to complete study evaluations
- 2) Severe cardiomyopathy/congestive heart failure (for MEP)
- 3) A pacemaker, any metal-based medical or non-medical implants/devices, any non-removable metal-based object (e.g. body piercings, jewelry, etc.) (for the CrCEST measures only)
- 4) Any history of intraocular injury or fragment in or around the orbit that cannot be cleared through radiologic evaluation (for the CrCEST measures only)
- 5) Any history of bullet, shrapnel, or stabbing wounds that cannot be cleared through radiologic evaluation (for the CrCEST measures only)
- 6) Claustrophobia or any known medical conditions which can be exacerbated by stress, anxiety, or panic attacks triggered by enclosed spaces (for the CrCEST measures and MEP only)
- 7) Inability to lie flat on a patient bed in an MRI machine for up to 90 minutes (for the CrCEST measures only)
- 8) Pregnancy (for the CrCEST measures and MEP only)

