Visit 7 (subject dependent) Subjects will be assessed by medical history, neurological tests (FARS, Timed 25 foot walk (T25W), Timed 1 and 6 minute walks, Timed up and go (TUG), Berg Balance scale (BBS), 9 hole peg test (9HPT), PedsQL, ADL score and ataxia disability scale), biochemical tests (frataxin level, platelet metabolic biomarkers), and physiological testing (CrCEST, MEP). Data will be collected over a one day visit.

Data will be analyzed by [name] and collaborators. No subject visits occur during this time.

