4 STUDY PROCEDURES

4.1 Neurological Outcome Measures

- a) Medical history: In the following description of study procedures, the term "patient" refers to individuals with Friedreich Ataxia. In order to obtain data and validate clinical outcome measures the following studies will be done. Quantitative and descriptive clinical data collection on all subjects, including medical history and medications. We will also try to obtain copies of subject's most recent Echocardiograms and EKG reports, as found in their medical records.
- b) Friedreich ataxia rating scale: The FARS is a rating scale based upon the clinical neurologic examination and will be administered by a neurologist who is masked to scores from the other measures. FARS ratings range from 0 to 125, based on summation of 25 different neurologic exam features.
- c) The timed 25-foot walk (T25W): A timed measure of how fast a subject walks 25 feet.
- d) The 9-hole peg test (9HPT): A timed test of how long it takes for a subject to place pegs in a standard pegboard. It also has an electronically measured version (the CCFS) and a "click test" in which patients click a button as fast as they can.
- e) Extended timed walking tests: A 1-minute timed walk and a 6-minute timed walk (but not to exceed 6 minutes in length) will be conducted. The timed 1-minute and 6-minute walks are quantitative mobility and leg function performance tests based on distance

traveled in one and six minutes, respectively. The subject is directed to one end of a clearly marked large rectangular course and is instructed to walk around as quickly as possible for one or six minutes. The distance is calculated by measuring how far the subject travels along the marked course. Subjects may use assistive devices during this task. The 1 minute walk will be performed twice, separated by 5 minutes of rest.

- f) Specific gait and balance tools utilized in other gait disorders of childhood, including the Timed Up and Go (TUG) and Berg balance scales (BBS). The TUG is a test of the time to rise from a chair, walk three meters (10 feet), turn around, walk balk to the chair, and sit down. It has previously been tested in older subjects with FRDA and has been used in both elderly populations and very young cerebral palsy cohorts. The BBS is a semiquantitative rating scale based on ability to stand sit and balance in various positions (5).

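### The device and metal exclusions apply to CrCEST alone, so the written criteria leave a child with an implanted device or cranial or orbital metal, but no severe cardiac disease, eligible for annual TMS

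*Combined protocol and SAP*

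**What the plan says.** Section 3.4.2 gives most exclusions a scope label. Three deal with devices or metal, and all three are confined to CrCEST:

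- Criterion 3: "A pacemaker, any metal-based medical or non-medical implants/devices, any non-removable metal-based object (e.g. body piercings, jewelry, etc.) (for the CrCEST measures only".
- Criterion 4: "Any history of intraocular injury or fragment in or around the orbit that cannot be cleared through radiologic evaluation (for the CrCEST measures only".
- Criterion 5: "Any history of bullet, shrapnel, or stabbing wounds that cannot be cleared through radiologic evaluation (for the CrCEST measures only".

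Where MEP is meant, the list says so. Criterion 2 reads "Severe cardiomyopathy/congestive heart failure (for MEP". Criterion 8 reads "Pregnancy (for the CrCEST measures and MEP only", and criterion 6 (claustrophobia and stress-related conditions) carries the same joint label. Section 3.4.1 adds a minimum weight of 10 kg for MEP.

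Section 4.5 describes MEP as TMS: a brief electromagnetic pulse directed at the motor cortex. It is offered to all CHOP participants, and 30 who meet the criteria are taken in order of arrival. Section 3.1.2 schedules it at 0, 12, 24 and 36 months. It also lists a further visit, "Visit 7 (subject dependent) Subjects will be assessed by medical history, neurological tests", whose tests include "biochemical tests (frataxin level, platelet metabolic biomarkers), and physiological testing (CrCEST, MEP".

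**The concern.** The label on criteria 3 to 5 does more than stay silent about MEP: it limits those criteria to the other procedure. Staff who apply the list as written have no stated ground to keep a child with a pacemaker, or with metal in the skull or orbit, out of the TMS subset. A child turned away from CrCEST for one of these reasons could still be taken into MEP.

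Two features of the protocol make the omission worth settling. Section 1.1 names cardiomyopathy as a characteristic of the disease, and criterion 2 shows that cardiac status is considered relevant to MEP. Criterion 2 turns on severity, however, so a child with a cardiac device but without severe disease falls outside it. Also, MEP is repeated over three years or more, so a child's device status could change between sessions.

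What is at stake is the clarity of a paediatric safety rule. No estimate or analysis in the plan depends on it.

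**Working it through.** The plan states no figure on this point, so the check is to read every criterion for its scope and its subject.

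| Criterion | Scope | Covers a device or metal? |
|---|---|---|
| Inclusion 4, weight | MEP | No |
| Exclusion 1, inability to complete evaluations | All | No |
| Exclusion 2, severe cardiomyopathy or heart failure | MEP | No |
| Exclusion 3, pacemaker, implants, metal | CrCEST | Yes |
| Exclusion 4, eye injury or orbital fragment | CrCEST | Yes |
| Exclusion 5, bullet, shrapnel, stabbing wounds | CrCEST | Yes |
| Exclusion 6, claustrophobia, stress-related conditions | CrCEST and MEP | No |
| Exclusion 7, inability to lie flat | CrCEST | No |
| Exclusion 8, pregnancy | CrCEST and MEP | No |

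Of the five listed criteria that can apply to MEP (inclusion 4; exclusions 1, 2, 6 and 8), none covers a device or metal. All three that do are confined to CrCEST. The remaining inclusion criteria (age, diagnosis, permission) do not touch the matter.

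Next, whether another section closes the gap:

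- Section 4.5 states no device or metal check before TMS.
- Section 5.2.1 describes telephone screening for contraindications and testing for metal objects, but ties both to MRI. The same paragraph says that all participants have a medical record review for conditions bearing on their safety. It attaches no MEP exclusion to what that review finds.
- Section 4.1 collects medical history on every subject and adds: "We will also try to obtain copies of subject's most recent Echocardiograms and EKG reports, as found in their medical records". This may reveal a device, but no action follows from it in the text.
- The TMS paragraph of section 5.2.1 names seizures, hearing and pain or discomfort as the main concerns. It does not mention implants or metal.

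**Exposure under the written rule** (an amount of stimulation, not a measure of harm). Inputs from section 4.5: about 20 to 30 stimuli to find the threshold and site, 20 test stimuli, and up to 30 optional repeats. I assume the threshold search is done at each session.

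- Per session without repeats: 20 + 20 = 40, to 30 + 20 = 50. Maximum with repeats: 30 + 20 + 30 = 80.
- Four scheduled sessions: 4 × 40 = 160, to 4 × 50 = 200; maximum 4 × 80 = 320.
- Five sessions, with Visit 7: 5 × 40 = 200, to 5 × 50 = 250; maximum 5 × 80 = 400.

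**Children affected.** The documents give no prevalence of devices or cranial or orbital metal. With assumed values of 0%, 1% and 5% among the 30 MEP children: 30 × 0 = 0; 30 × 0.01 = 0.3; 30 × 0.05 = 1.5.

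**The case against.** The strongest reply is that the documents supply no hazard. They nowhere call TMS unsafe with a pacemaker or with metal. Section 5.2.1 regards single-pulse TMS in children as minimal risk, citing more than 100 studies in more than 800 normal and more than 300 neurologically abnormal children with no serious adverse events. On that reading, MRI-type criteria labelled for an MRI procedure are deliberate scoping. This stands as a limit on the strength of the point. It does not remove it: the safety summary does not say whether any of those children had a device or cranial metal, and the protocol gives no reason for leaving them eligible.

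A second reply is that the general record review, the medical history at every visit and the request for cardiac reports would find such children, and that a safety screen implies acting on its findings. In practice that may be so. It remains an inference, because no written MEP exclusion follows from a positive finding. The MEP procedure is also said to be used in other approved CHOP studies, whose screening arrangements cannot be seen here.

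Four stronger readings are tempting and are not supported:

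- That staff would stimulate such a child. The text shows eligibility on paper only.
- That harm is demonstrated. No hazard is described or quantified.
- That MEP has no exclusions of its own. It has several; they do not cover devices or metal.
- That the list contradicts itself. No two statements conflict; this is an omission in scope.

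**Conclusion.** The point holds as a gap in the scope of the written eligibility rule: a child with an implanted device or cranial or orbital metal, who passes the weight, ability, cardiac, claustrophobia and pregnancy criteria, is eligible for annual TMS. The reading of the labels is certain. The practical size is not: under the assumed 0% to 5%, it is between none and one or two of the 30 MEP children, and zero is quite possible. No planned analysis changes. It is worth correcting because the rule concerns children, the procedure is repeated, and the correction is cheap.

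**What to change.** In section 3.4.2:

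- Split criterion 3. Give two parts the joint CrCEST and MEP label already used for criteria 6 and 8: (a) *a pacemaker or other implanted electronic device*; (b) *metal implants in the skull or brain (fixed dental or orthodontic metal does not exclude from MEP)*. All other metal, including dental metal, stays excluded for CrCEST only.
- Leave orbital fragments to criterion 4 alone. Relabel it for CrCEST and MEP and keep its radiologic-clearance condition, so that no second rule bars a fragment that has been cleared.
- Extend criterion 5 to MEP for cranial or orbital wounds that cannot be cleared radiologically. Other wounds stay under CrCEST only.

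In section 5.2.1, add: *Before each TMS session, the medical history already taken at the visit is used to check for implanted devices and for metal in the skull, brain or orbit.*

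The dental exemption and the line between cranial and other metal are proposals of this review, which the TMS team should confirm. If the sponsor means to allow TMS in these children, a sentence giving the reason would serve instead.

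Cost: edits to three criteria, one added sentence, and one question per MEP visit, which is 30 × 4 = 120 questions, or 30 × 5 = 150 if every MEP child has Visit 7. Possibly a very small number of the 30 places would be lost (0 to 1.5 under the assumption above). Replacements could come only from consenting, eligible CHOP participants outside the subset, at most 90 − 30 = 60, and a late replacement might not complete the annual series.

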4 STUDY PROCEDURES

4.1 Neurological Outcome Measures

- a) Medical history: In the following description of study procedures, the term "patient" refers to individuals with Friedreich Ataxia. In order to obtain data and validate clinical outcome measures the following studies will be done. Quantitative and descriptive clinical data collection on all subjects, including medical history and medications. We will also try to obtain copies of subject's most recent Echocardiograms and EKG reports, as found in their medical records.
- b) Friedreich ataxia rating scale: The FARS is a rating scale based upon the clinical neurologic examination and will be administered by a neurologist who is masked to scores from the other measures. FARS ratings range from 0 to 125, based on summation of 25 different neurologic exam features.
- c) The timed 25-foot walk (T25W): A timed measure of how fast a subject walks 25 feet.
- d) The 9-hole peg test (9HPT): A timed test of how long it takes for a subject to place pegs in a standard pegboard. It also has an electronically measured version (the CCFS) and a "click test" in which patients click a button as fast as they can.
- e) Extended timed walking tests: A 1-minute timed walk and a 6-minute timed walk (but not to exceed 6 minutes in length) will be conducted. The timed 1-minute and 6-minute walks are quantitative mobility and leg function performance tests based on distance

traveled in one and six minutes, respectively. The subject is directed to one end of a clearly marked large rectangular course and is instructed to walk around as quickly as possible for one or six minutes. The distance is calculated by measuring how far the subject travels along the marked course. Subjects may use assistive devices during this task. The 1 minute walk will be performed twice, separated by 5 minutes of rest.

- f) Specific gait and balance tools utilized in other gait disorders of childhood, including the Timed Up and Go (TUG) and Berg balance scales (BBS). The TUG is a test of the time to rise from a chair, walk three meters (10 feet), turn around, walk balk to the chair, and sit down. It has previously been tested in older subjects with FRDA and has been used in both elderly populations and very young cerebral palsy cohorts. The BBS is a semiquantitative rating scale based on ability to stand sit and balance in various positions (5).
- g) The Pediatric Quality of Life (PedsQL) and the FARS ADL scores. Subjects aged 2-7 inclusive will not need to complete a PedsQL scale. The PedsQL scale is the Pediatric Quality of Life Inventory. This scale has two separate questionnaires: one is designed for subjects between the ages of 8-12, the other for subjects between 13-18. The subject will answer the questionnaire with the help of the study coordinator. The subject's parent or guardian will also answer a separate questionnaire on the same topic. The FARS ADL score is a similar questionnaire asking the participant how they view their performance on tasks such as dressing, bathing, etc. Subjects and their guardians will be asked to complete questionnaires annually.

In some situations, such as a global pandemic, travel restrictions, as well as poor health or an overall concern for safety, it may not be possible for subjects to have an in-person visit every year. Under these circumstances, for subjects who have previously consented for this study it is possible to conduct a visit remotely via phone or video/telehealth. A remote visit will not include the 9HPT or any sample collection. Remote visits can include the following: review of consent forms, medical history and medications, completion of questionnaires that can be mailed or emailed to subjects, certain assessments of gait and motor functioning including answers to the surveys which ask questions about gait and motor abilities, parts of the FARS exam (for example, the Bulbar facial nerve function exam which can be performed and viewed over video), and timed standing and/or walking tests that can be viewed over video (provided that it has been determined ahead of time to be a low fall risk to the subject - fall risk will be determined by taking a recent detailed fall history of each subject prior to any standing or walking test).

All procedures detailed above (except the BBS and TUG) have been included on other IRB approved studies at CHOP, including a currently open study (IRB 01-002609).

4.2 Blood Draw for Frataxin Protein Assay, and Platelet Metabolic Biomarkers

A standard venous blood draw is performed by a trained phlebotomist or equivalently trained study coordinator or nurse. No more than 40 ml whole blood will be collected from study subjects, which is a smaller amount than the NIH-recommended limit for all but the smallest children and below the NIH-recommended maximum limit for children. The maximum amount of blood collected from a participant will be determined based on either the above maximum volumes or based on the maximum amount of sample allowed based on weight (2cc/kg), whichever volume is lower, for safety purposes samples collected from subjects will not be sent to each laboratory involved in the study.

The sample will be used for the blood frataxin protein assay, and platelet metabolomics biomarkers. The samples are fractionated in [name] lab and are either frozen for frataxin analysis, or incubated with C13 metabolic precursors, then frozen for platelet metabolic assay. Both are performed in [name] lab at the University of Pennsylvania.

5 ml of blood will be used for frataxin dipstick analysis. Immediately after the blood draw, the blood will be transported and stored at -80 degrees Celsius in the lab of [name]. The sample remains in the freezer until it is ready to be analyzed. Specimen collections will function as exploratory measures and will be determined by lateral flow assay in samples from whole blood. These samples will be analyzed by a trained laboratory technician in the lab of [name].

When samples are to be analyzed by outside laboratories, they will be shipped on dry ice according to proper guidelines. Samples will be sent with elements of dates labeled on tubes (date of collection). Each sample will be given a unique number.

4.3 Buccal Swab Collection

Sterile, disposable Epicentre MasterAmp Buccal Swab Brushes will be used to isolate buccal cells (cells lining the mouth) from the inner cheek as suggested by the manufacturer. The procedure is very gentle and causes no discomfort. The inner cheeks are first gently cleansed by light brushing with a new moist, soft toothbrush and then rinsed with a sip of water. An Epicentre MasterAmp Buccal Swab Brush is then gently but firmly used to brush both cheeks, collecting a light layer of easily sloughed-off epithelial cells on the surface of the brush. Exfoliated cells are then transferred to ice-cold extraction buffer preloaded in a small sample collection tube. The sample is then immediately coded and processed for frozen storage in [name] laboratory. The specimen is analyzed by lateral flow assay and performed by a trained laboratory technician.

As with the frataxin blood sample, the cheek swab will be processed in [name] lab. Samples from other sites will again be shipped on dry ice according to proper guidelines. Samples will not be sent with any PHI. Again, the purpose of sending the samples to [name] lab at CHOP is to ensure that similar results are obtained on this assay across multiple locations. This is required to validate the assay.

4.4 Magnetic Resonance Imaging (MRI) muscle phenotyping

At CHOP, 12 of the approximately 90 participants will be included for muscle phenotyping assessment as part of the study's aim to define the progression of physiological dysfunction in affected tissues. All participants will be offered the opportunity to participate, but 12 children will be selected on a first-come basis and must meet inclusion criteria. 12 children will participate in the protocol and be studied annually at 0, 12, 24, and 36 months, unless the subject wishes to complete their annual visit remotely. Creatine chemical exchange saturation transfer (CrCEST) is a technique that will be carried in the same session as ³¹P Magnetic Resonance Spectroscopy (MRS) at CHOP using a 3-Tesla Magnet. ³¹P MRS is an established method to measured oxidative phosphorylation (OXPHOS) in muscles. Briefly, the rate of creatine recovery (CrCEST) or phosphocreatine (PCr) resynthesis (PCrr, ³¹P MRS) was estimated, each after a 3-minute bout of plantar extension/flexion exercises. These studies showed that CrCEST produced similar results with respect to recovery kinetics, but offered superior anatomical resolution (6).

The participant will safely lie on an MRI bed and a coil will be placed around part of the body under investigation. The study participant may also wear ear-plugs to reduce the volume of MRI signal noise. They will then be moved directly into the magnet so that the body part under investigation is observable through the MRI program. The procedure will

proceed with the study team conducting communication with the participant via a two-way radio communication system. We will employ resting and post-exercise chemical exchange saturation transfer (CrCEST) to assess muscle OXPHOS capacity. During the session, we will ask subjects to perform several brief sub-maximal leg exercises (about 5 minutes in total). Subjects will be asked to press down on a pedal, similar to a car accelerator or piano foot pedal, approximately 90 times, or as many as they are able, over a 2 minute period. A member of the study team will remain in contact with the subject through a two-way intercom and will count aloud each repetition. A certified medical professional will continue to closely monitor the patient for safety and any sign of discomfort during the MRI procedures. Time in the MRI machine will not exceed 90 minutes. After completion of the imaging, they will be carefully and slowly removed from the MRI machine to prevent any lightheadedness caused by orthostatic hypotension.

Creatine CEST imaging sequence will be used to assess creatine distribution and concentrations in muscle (lower extremity), both at rest and after recovery from a brief foot pedal depression exercise (7,8). The CrCEST sequence is based on a standard single-slice FLASH pulse sequence with prep saturation pulses in front. The acquisition time for the CEST sequence is only about 30 seconds, but we need to acquire the images at varying saturation amplitude and pulse duration. Typical parameters used are: slice thickness = 8 mm, flip angle = 10° , TR = 5.6 ms, TE = 2.7 ms, field of view = $140 \times 140 \text{ mm2}$, matrix size = 128×128 .

If time permits, we will also perform mechanical and structural properties of bone (lower extremity) using MRI and finite element analysis. This test takes less than 10 minutes and will be added on at the end of the standard sequence in patients who have time

The CrCEST MRI sequences performed for this protocol are non-FDA approved and are therefore considered experimental. The bone strength MRI sequence is part of an FDA-approved sequence but its use is being re-purposed for the study, which requires special post-processing techniques. Results from the FDA-approved bone strength sequence will be entered into the medical record, but results from the non-FDA approved CrCEST research sequence will not. If we identify any incidental findings from non-investigational MRI sequences, we will evaluate them to determine if medical attention is needed. In addition, subjects have the option to have any findings forwarded to their primary care provider for review.

The procedure detailed above has been included on other IRB approved studies at CHOP, including an open study in mitochondrial disease by co-investigator [name] (IRB 15-012445).

